Beside the salary for [name] and two research nurses mentioned above, we apply the Danish Cancer Society for expenses related to MRI scans. The departments will hold expenses for CT scans for the 50% of the patients that are expected to have more than 14 days between CT and MRI. Please see the attached budget for more details.

FUTURE PERSPECTIVES

We expect this project to substantially improve our ability to tailor the optimal treatment for each individual with pancreatic cancer. Underdiagnosis of liver metastases delays the initiation of life-prolonging chemotherapy. Thus, with proper preoperative detection of liver metastases, our project will improve both survival and quality-of-life, as patients will be spared from unnecessary major surgery. Thus, findings from our project is expected to have an immediate clinical impact. Furthermore, if MRI is non-inferior to CT with respect to tumor staging, it may replace CT in the diagnostic workup of pancreatic cancer patients.

ETHICAL CONSIDERATIONS

This project will be conducted according to the Helsinki Declaration. The project needs to be registered at the Danish Data Protection Agency in accordance with the Central Denmark Region common registration system and it also requires approval from the Central Denmark Region Ethics Committee. We will ensure that all permissions are granted when study starts. All information involving patients will be handled according to national law on personal data information. Both positive, negative, and inconclusive results will be published, and presented at scientific meetings. Results will be presented at international scientific congresses, and we will aim for publications in

high-impact journals with focus on oncology, radiology, and surgery. The study will be registered at ClinicalTrials.gov and monitored by the Good Clinical Practice Unit at Aarhus University Hospital.

REFERENCES

- Gillen S, Schuster T, Meyer Zum Buschenfelde C, Friess H, Kleeff J.
 Preoperative/neoadjuvant therapy in pancreatic cancer: a systematic review and metaanalysis of response and resection percentages. PLoS Med. 2010;7: e1000267.

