MAGIPAC trial: Magnetic Resonance Imaging for Better Selection of Pancreatic Cancer Patients for Surgery: A Randomized Clinical Trial.

BACKGROUND AND SIGNIFICANCE

Pancreatic cancer has a dismal prognosis with a 5-year survival of only 8% [1]. Despite surgery being the only chance for cure, only 20% of the patients are eligible for surgical treatment, as most have metastatic disease at diagnosis [2]. Pancreatic cancer surgery is a major procedure with a substantial morbidity and mortality [3]. Therefore, it is important to avoid futile resections that will delay initiation of life-prolonging chemotherapy in patients who will not benefit from surgery. Whether the patient can be operated depends on the local extent of the tumor and the presence of distant metastases (most often in the liver), which are contraindications to surgery [4-6].

Currently, computed tomography (CT) is state-of-the-art for assessing pancreatic cancer resectability [7]. However, CT has some shortcomings. Although it performs well in assessing the local extent of the tumor, it has limited sensitivity for detecting small liver metastases in pancreatic cancer [8]. Relying solely on CT imaging therefore leads to futile resections in patients with undetected liver metastases. This will impair survival, as patients will have to recover from surgery and the associated complications before they can initiate chemotherapy. These shortcomings may be overcome by using liver and pancreatic magnetic resonance imaging (MRI) instead of CT.

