MRI may be superior to CT for detection of liver metastases in pancreatic cancer [9]. As liver metastases from resectable pancreatic cancer tend to be small [10], for which MRI (with use of diffusion weighted imaging and liver-specific contrast) has a high sensitivity, routine use of preoperative MRI could be beneficial. However, the feasibility of using MRI in detection of liver metastases in pancreatic cancer patients has been sparsely investigated. One prospective study of 69 pancreatic cancer patients found that almost 25% had liver metastases on MRI that were not visible on CT [11], whereas a retrospective study of 216 patients found that MRI revealed liver metastases in only 5% of patients with CT-assessed non-metastatic pancreatic cancer [12]. The latter study also found a longer time to recurrence after surgery in patients undergoing preoperative MRI, suggesting that preoperative MRI may be beneficial in pancreatic cancer patients. However, they did not provide information on why MRI was performed, and findings are unlikely to be generalizable. Furthermore, only few studies have examined the use of MRI in assessing the local extent of the tumor, suggesting it is not inferior to CT [13, 14].

Thus, MRI may provide a superior alternative to conventional CT in order to improve treatment allocation for pancreatic cancer patients. However, there is a substantial need for high-

quality research to examine this. Specifically, no randomized clinical trial (RCT) has been conducted.

PURPOSE AND OVERALL AIM

[figure not shown]
We propose to conduct a nationwide RCT to examine the feasibility of using MRI for tumor staging and identification of liver metastases in pancreatic cancer patients. *The aim is to improve selection of pancreatic cancer patients for surgery in order to increase overall survival*. Within this RCT, we will conduct three studies outlined below.

STUDY POPULATION AND DESIGN

Patients

200 patients with CT-assessed resectable pancreatic cancer allocated to surgery by the local multidisciplinary tumor board (MDT) will be included. Patients will be randomized to either the intervention (preoperative MRI, n=100) or control/standard-of-care (no preoperative MRI, n=100) arm.

Study design and patient flow

An overview of the proposed study design is shown in Figure 1.

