Upon consent, patients will be electronically randomized to one of the two treatment arms. Patients in the control arm will proceed directly to surgery. Patients in the intervention arm will have an MRI performed after randomization and before treatment. If the interval from CT to MRI is >14 days, a new CT will be performed to assure a valid comparator. The MRI will be read by an experienced gastro-radiologists blinded to the patient's identity and initial CT scan. Based on the MRI, the treatment decision will be made (*Figure 2*):

Figure 1. Study design. R: Randomization.

- 1) No liver metastases on MRI (expected ~75%): Surgery as planned.
- 2) Non-specific liver lesions on MRI, not seen on CT (expected $\sim 10\%$): Surgery as planned.
- 3) Liver metastases on MRI (expected ~15%): Referral to liver biopsy and oncological treatment if malignancy is verified. If biopsy is inconclusive, repeat liver MRI after one month.

[figure not shown]

Figure 2. Patient flow in the intervention arm. MDT: Multidisciplinary team conference.

Follow-up

Patients will be followed for up to three years for information on treatment, recurrence, and vital status. We will conduct standard-of-care follow-up CT at 3, 6, 9, 12, 18, 24, 30, and 36 months postoperatively in all patients. Primary end-point for this project will be one-year survival. For subsequent studies, we will also perform analyses of three-year survival.

SPECIFIC STUDY AIMS, HYPOTHESES AND OUTCOMES

Study I: To compare tumor staging of pancreatic cancer patients assessed by MRI versus upper abdominal CT.

Study II: To assess the ability of MRI to detect liver metastases in pancreatic cancer patients with resectable tumor on CT.

Study III: To assess the impact of MRI on treatment allocation, recurrence, and survival in pancreatic cancer patients with a resectable tumor on CT.

Details of study hypotheses, population, and analytical plans are outlined in Figure 3.

	Study I	Study II	Study III
Aim	To compare tumor	To assess the ability of	To assess the impact of
	staging of pancreatic	MRI to detect liver	MRI on treatment
	cancer patients assessed	metastases in pancreatic	allocation, recurrence,
	by MRI versus upper	cancer patients with	and survival in pancreatic
	abdominal CT	resectable tumor on CT	cancer patients with a
			resectable tumor on CT
Hypothesis	MRI is non-inferior to CT	MRI will detect liver	Use of MRI will change
	with respect to tumor	metastases in patients	treatment allocation and

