	staging	with a resectable tumor	improve overall survival
		on CT	
Population	Patients in the	Patients in the	Patients in both arms
	intervention arm (N=100)	intervention arm (N=100)	(N=200)
Analysis	Agreement assessed by	Agreement assessed by	Treatment allocation and
	intraclass correlation	intraclass correlation	recurrence by Chi ² test
	coefficient (ICC)	coefficient (ICC)	Survival analyses by
			Kaplan-Meier estimation

Figure 3. Outline of the three studies.

POWER CALCULATIONS AND FEASIBILITY

Assuming alpha=0.05, power of 80%, and a hazard ratio of death of 1.5, we need 191 patients in total. To guard against dropout of 5%, we aim to include 200 patients. On average, all four institutions performing pancreatic cancer surgery in Denmark (Rigshospitalet, Aarhus, Aalborg, and Odense) shall include 50 patients. We aim to finalize patient enrollment during the first 18 months of the study period, equaling to 2.8 patients monthly in each institution. In total, ~300 resections will be performed during this 18-month period. We consider it feasible and realistic to include two-thirds of these patients.

IMAGING PROTOCOLS

CT imaging protocol

As a part of the routinely workup for staging pancreatic cancer, all patients referred to the local hepato-pancreato-biliary MDT board undergo a pancreas-specific CT scan. All CT scans include a

portal venous phase (PVP) of the liver. CT scanners from different vendors will be used to acquire the images. The PVP will routinely obtained by 120 KV and mAs range from 150 to 290 depending of the body mass of the patient and the scan system. Contrast medium will be administered intravenously as a bolus injection by weight bases contrast Iodine concentration of 500 – 750 mg I/kg and a rate of 3-5 ml/s, followed by a saline flush of 20–40 ml. The scan delay for the PVP will be 50 sec (post-threshold, bolus tracking). Axial slice thickness of 2 mm slices will be reconstructed with 1 mm increments.

MR imaging protocol

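### Study I cannot test whether MRI is non-inferior to CT on the calls that decide operability, because CT had already called every enrolled patient resectable; a conclusion about replacing CT does not follow

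*Combined protocol and SAP*

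**What the plan says.** Under Study Population and Design (Patients), entry depends on the CT result: "200 patients with CT-assessed resectable pancreatic cancer allocated to surgery by the local multidisciplinary tumor board (MDT) will be included". Study I draws its 100 patients from the intervention arm of that group.

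The aim of Study I is "To compare tumor staging of pancreatic cancer patients assessed by MRI versus upper abdominal CT". Unlike the aims of Studies II and III, it is not limited to patients with a resectable tumor on CT. Figure 3 gives the hypothesis that "MRI is non-inferior to CT" for staging, and the analysis as "Agreement assessed by" the intraclass correlation coefficient (ICC). It states no margin and no reference standard for stage.

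Future Perspectives then says of MRI, should non-inferiority be shown: "it may replace CT in the diagnostic workup of pancreatic cancer patients". According to Background and Significance, "only 20% of the patients are eligible for surgical treatment, as most have metastatic disease at diagnosis".

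Two further provisions matter. Study Design and Patient Flow requires a new CT when more than 14 days separate CT and MRI, and the paragraph on expenses just before Future Perspectives expects this in 50% of patients. The section on metastatic lesions grades each focal liver lesion on a 3-point scale of confidence in malignancy.

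**The concern.** A non-inferiority claim must be able to fail. Here it would fail if CT showed disease that MRI missed. Patients in whom CT shows metastases or a locally unresectable tumor are not enrolled and have no study MRI, so the evidence that could count against MRI on these calls is removed before the study starts. Neither a better agreement statistic nor a fuller MR protocol would bring it back.

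At stake is what Study I may conclude. Its result would be carried over to the workup of pancreatic cancer patients in general, most of whom are outside the enrolled group by the protocol's own account. The plan does not mention this limit.

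**Working it through.** **Plan's own figure.** There is none for Study I. The only sample-size figure, 191, belongs to the survival comparison. It reproduces as 4 × (1.960 + 0.842)² / (ln 1.5)² = 191, which is a number of deaths under Schoenfeld's formula, and it has no bearing on Study I.

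**Step 1: the two-by-two table on the entry CT.** Take the liver pathway in Study Design and Patient Flow as an example, with about 15% MRI-positive and the other 75% + 10% = 85% not called metastatic. Per 100 patients:

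| | MRI positive | MRI negative |
|---|---|---|
| CT positive | 0 | 0 |
| CT negative | 15 | 85 |

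The top row is empty because of the entry criterion, not because of anything MRI does. The same holds for local unresectability.

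**Step 2: what the planned statistic shows.** Let CT be 0 in all n patients and let MRI be positive in a proportion p, with 0 < p < 1.
- Between-patient mean square: n·p(1−p) / [2(n−1)].
- Residual mean square: n·p(1−p) / [2(n−1)].
- The ICC numerator is the difference between the two, so ICC = 0.
- For kappa, observed agreement is 1−p and chance agreement is also 1−p, so kappa = 0.

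With n = 100 and 5, 15 or 25 MRI positives, both statistics are 0. They carry no information about MRI's miss rate.

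**Step 3: can the enrolled sample tell a poor MRI from a good one?** Assumptions, none from the documents: CT sensitivity 80%, specificity 95% for both modalities, errors independent given true status. The share truly unresectable is varied over 30%, 50% and 80%. The formulas, with prevalence π and MRI sensitivity s, are:
- CT-only positives per 100 unselected: 100 × [π × 0.8 × (1−s) + (1−π) × 0.05 × 0.95].
- MRI-only positives per 100 enrolled: 100 × [π × 0.2 × s + (1−π) × 0.95 × 0.05] / [π × 0.2 + (1−π) × 0.95].

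| Truly unresectable | MRI sensitivity | CT-only, unselected | CT-only, enrolled | MRI-only, enrolled |
|---|---|---|---|---|
| 30% | 50% | 15.3 | 0 | 8.7 |
| 30% | 90% | 5.7 | 0 | 12.0 |
| 50% | 50% | 22.4 | 0 | 12.8 |
| 50% | 90% | 6.4 | 0 | 19.8 |
| 80% | 50% | 33.0 | 0 | 25.6 |
| 80% | 90% | 7.4 | 0 | 43.9 |

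In an unselected sample, the CT-only column separates the inferior MRI from the better one. In the enrolled sample it is 0 in every row.

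**Step 4: the group left out.** If 20% of patients are eligible for surgery, 100 enrolled correspond to 100/0.20 − 100 = 400 not enrolled. Assume that all 400 have a CT finding that rules out surgery. An MRI miss rate of 5%, 10% or 30% would then give 20, 40 or 120 CT-only findings, none of them in the study.

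**Step 5: the repeat-CT window.** About 100 × 0.50 = 50 patients. Assume that the repeat CT is newly positive in 2% to 10%, and that MRI misses 10% to 50% of those.
- Low end: 50 × 0.02 × 0.10 = 0.1 expected CT-only findings; chance of none (1 − 0.002)^50 = 0.905.
- High end: 50 × 0.10 × 0.50 = 2.5 expected; chance of none (1 − 0.05)^50 = 0.077.

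The window exists, but it is too small to settle the question.

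**The case against.** Four arguments limit the point.

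**No built-in win for MRI.** A reader might infer that the design guarantees a result in MRI's favour, whatever its accuracy. The plan does not support that. Study I is analysed by agreement, and MRI calls that go beyond CT are disagreement. On operability calls the planned result is uninformative (Step 2), not favourable. A head-to-head detection count is not what Study I plans.

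**Study I is not empty.** Its subject is tumor staging; liver metastases are the aim of Study II. Differences in graded local stage within resectable disease can go either way and can be compared in all 100 patients. Liver lesions graded on the 3-point scale may also differ either way, since no stated criterion excludes patients with benign or indeterminate lesions on CT. This stands. It does not rescue local unresectability, which is also constant on the entry CT.

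**CT is not constant for everyone.** In about half the arm the comparator is a repeat CT that did not decide entry. This also stands, within the limits of Step 5.

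**The sentence is tentative.** It is conditional, cautiously worded, placed under Future Perspectives, and triggers no analysis or decision. This lowers the severity, but the condition is still one that this sample cannot establish for the calls that matter most to it.

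The sensitivities in Step 3 are illustrative and run against the protocol's premise that CT is weak and MRI strong for small liver metastases. The empty CT-only cell does not depend on them.

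**Conclusion.** The point holds for the calls that decide operability. On the entry CT, the number of findings CT sees and MRI misses is 0 by design, agreement on these calls is uninformative, and non-inferiority cannot be tested whatever MRI's true miss rate. This follows from the entry criterion alone. The repeat CT adds an expected 0.1 to 2.5 such findings, on assumed rates. The extension to replacing CT in the general workup is therefore wrong as written.

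It would go too far to say that Study I as a whole is invalid or biased toward MRI: graded staging within CT-resectable disease remains a fair comparison in all 100 patients. The randomised survival comparison in Study III is not affected. Severity: should-fix.

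**What to change.** - Restate Study I as two objectives: (a) the added staging yield of MRI after a CT showing resectable disease, and (b) a CT-MRI comparison of graded local staging within CT-resectable patients, using all 100.
- Drop the non-inferiority claim for resectability and metastasis status.
- Limit the sentence in Future Perspectives to MRI as an add-on after CT in CT-resectable patients.
- If a two-way comparison of operability calls is wanted, use only the repeat-CT reads (about 50 patients) and label it exploratory. State that these patients are preselected twice: on the first CT, and by a delay of more than 14 days.

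This needs no new patients or scans, only rewording and, if wanted, one subset analysis on scans already planned. The price is a narrower claim. A claim about replacing CT would need a different study, with paired CT and MRI before the resectability decision, a reference standard and a stated margin.
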